14. Are not able to attend face-to-face visits at the study site or plan to move out of the area prior to the 3-month LTFU visit.
15. Have any current problem, which in the opinion of the Investigator or Medical Monitor, might interfere with the individual's participation in the study or confound the assessment of safety and/or efficacy of the study drug.

Statistical Methods:

Descriptive statistics will assess the frequency of AEs or SAEs, laboratory parameters, and vital signs. Change in clinical and epigenetic outcomes will be measured from pre-treatment (baseline) to Study Day 7. Other exploratory endpoints will be assessed based upon changes from baseline for various quality-of-life (continuous) questionnaires, changes in sleep-related and other physiological measurements will be tracked using a wearable device. Plasma concentrations and PK parameters of psilocin will be summarized by descriptive statistics and graphically.

TABLE OF CONTENTS

1. LIST OF ABBREVIATIONS..... 14

2. BACKGROUND AND STUDY RATIONALE 17

2.1. Background 17

2.2. Study Purpose 17

2.3. Supporting Information 17

2.3.1 Condition..... 17

2.3.2 Psilocybin as a Potential Treatment for patients with PTSD 19

2.4. Rationale for Dose Selection..... 19

3. OBJECTIVES..... 20

3.1. Primary Objective 20

3.2. Secondary Objective 20

3.3. Exploratory Objectives..... 20

4. INVESTIGATIONAL PLAN..... 20

4.1. Study Design 20

4.2. Premature Discontinuation..... 25

4.3. Study Duration 25

4.4. Study Endpoints 25

4.4.1 Primary Endpoints 25

4.4.2 Secondary Endpoints 26

4.4.3 Exploratory Endpoints 26

5. PARTICIPANT ELIGIBILITY, ENROLLMENT AND WITHDRAWAL..... 27

5.1. Description of the Population..... 27

5.1.1 Inclusion Criteria 27

5.1.2 Exclusion Criteria 28

5.2. Participant Numbering 29

5.3. Withdrawal of Participants..... 29

6. STUDY DRUGS 30

6.1. Product Description..... 30

6.2. Packaging and Labeling 30

6.3. Product Storage and Handling	30
6.4. Product Stability.....	31
6.5. Dose and Administration	31
6.5.1 Dose.....	31
6.5.2 Route of Administration & Fasting State Prior to Dosing.....	31
6.6. Product Supply and Accountability	31
6.7. Allowed and Prohibited Medications and Therapies	31
6.7.1 Prohibited Medications/Treatments	31
6.7.2 Permitted Psychotherapy.....	31
7. STUDY PROCEDURES AND EVALUATIONS	32
7.1. Timing of Procedures	32
7.1.1 Recruitment of Participants.....	32
7.1.2 Pre-screening.....	32
7.1.3 Screening Period (Day -30 to -1).....	36
7.1.4 Study Day 1.....	38

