Unless a finding is made that excludes a participant from the trial, they will be evaluated by appropriately trained assessors for multiple psychological factors and assessments (including the LEC-5 and the PCL-5), some of which will determine the participant's eligibility as well as establish baseline measures for comparison pre- and post-treatment of exploratory objectives.

Participants will be required to complete several self-assessment quality-of-life (QoL) and patient reported outcome (PRO) instruments. They also will be provided with a health tracking wearable device to monitor several variables such as total daily steps, sleep parameters as well as heart rate and blood pressure. [If a participant already owns a suitable health tracking wearable device, they may use their own instead of the device provided for the trial.]

Participants that qualify for treatment will undergo individual preparatory training wherein each participant will be assigned to trained facilitators to build trust and rapport and receive education on the potential effects of psilocybin mushrooms. A Lead Therapist also will conduct a group education session regarding the treatment and take part in a ceremony following the individual preparation session.

Participants will be asked to bring their pain medication to the study site on Study Day 1, the dosing day. They will be educated on how the pain will be managed and they will not be prohibited from being administered additional pain medication should their pain increase following administration of the study drug. Patients who use opioid analgesics will be instructed to maintain their usual regimen.

- To the extent possible, input will be obtained from the participant's regular clinical providers on appropriate pain management for the participant during the trial, particularly in the case of analgesics associated with adverse reactions of concern with psilocybin (e.g., QTc prolongation with methadone).

During the screening period if a participant is found to have serious anxiety attack or another psychotic episode then the participant is referred to the relevant psychiatrist or responsible physician for follow up and treatment. Additionally, if the participant develops any medical emergency he/she will be managed as per the procedures described in detail under section 9.5.

Treatment Period:

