5.1.2 Exclusion Criteria

1. Currently uncontrolled hypertension. ($>140/90$ at Screening and $>145/95$ on Study Day 1).
2. History of recent seizure (within 3 months of Study Day 1).
3. History of stroke or transient ischemic attacks.
4. Preexisting history of valvulopathy or pulmonary hypertension.
5. A marked prolongation of QT interval (i.e., $QT \geq 450$ msec) over a series of 3 ECGs performed within 5-6 minutes.

CONFIDENTIAL

6. Currently uncontrolled diabetes ($HbA1c > 8.0\%$).
7. Potential for adverse drug-drug interactions such as the use of centrally-acting serotonergic agents within 24 hours prior to and for 72 hours following study drug administration on Study Day 1.
8. Significant suicide risk defined by (1) suicidal ideation as endorsed on items 4 or 5 on the Columbia Suicidal Severity Rating Scale (C-SSRS) within the last 6 months, at Screening, or at Baseline (Visit 1), or; (2) suicidal behaviors within the last 12 months as assessed by C-SSRS.
9. Patients with severe anxiety and depression measured as following: Participants with scores of 15 & above on Generalized Anxiety Disorder-7 (GAD-7) scale, and/or with scores of 20 & above on Patient Health Questionnaire-9 (PHQ -9).
10. Are pregnant or nursing or are women of childbearing potential who are not practicing a highly effective means of birth control.
11. Have any allergies or contraindication to psilocybin mushrooms.
12. Current users of psilocybin, LSD, DMT, Ayahuasca, Peyote, mescaline, and ketamine over the past 30 days will not qualify for the study unless the use of these agents is stopped for 30 days prior to Study Day 1 and the participant agrees to not use these (or similar) agents for 30 days after Study Day 1.
13. Are not able to attend face-to-face visits at the study site or plan to move out of the area prior to the 3-month LTFU visit.
14. Have any current problem that, in the opinion of the Investigator or Medical Monitor, might interfere with an individual's participation in the study or confound the assessment of safety and/or efficacy of the study drug.

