9. GAD-7: If a participant's score is ≥15 at Screening or on Study Day 1 (prior to study drug administration), the participant is not eligible for treatment.
10. PHQ-9: If a participant's score is ≥20 at Screening or on Study Day 1 (prior to study drug administration), the participant is not eligible for treatment.
11. C-SSRS: If at Screening or on Study Day 1 a participant's 'suicidal' assessment is scored as Category 4 (i.e., Active Suicidal Ideation with Some Intent to Act, without Specific Plan) or Category 5 (Active Suicidal Ideation with Specific Plan and Intent), the participant is not eligible to continue to participate in the trial and should be referred for appropriate psychiatric care.
12. POMS: On Study Day 1, after all protocol-mandated activities are complete, the clinician will assess the result of the POMS. If the posttreatment POMS score is not ≤125% of the baseline, pre-dose, value, the patient should be held overnight for observation. [Otherwise, if the score is ≤125% of the baseline, and if there are no other problems, the patient may be discharged to home (accompanied by a trusted adult).
13. AUDIT / DUDIT: The AUDIT and DUDIT should be completed at the Study Day 30 / End-of-Treatment visit if a participant prematurely discontinues from the trial (for any reason) and will not undergo the 3-month, Long-Term Follow-up visit.
14. ◆: The diamond reflects tests, examinations, assessments or other procedures that are to be completed the EoT visit if a participant is prematurely discontinued from further involvement in the trial and the particular protocol-mandated activity was not performed at the Study Day 8 visit.
15. **The One-to-One session as well as the Group session require participants to return to the study site on separate days. [Thus, the Screening Period can require three (3) visits to the study site.]**

Table 2
Study Day 1 Schedule of Events

Activity	Pre-Dose	Dose		Post Dose							
		Time 0	30 mins	60 mins	90 mins	120 mins	150 mins	180 mins	240 mins 4 hours	4.5, 5.0, 5.5, 6.0, 6.5, 7.0 and 7.5 hours	480 mins 8 hours
Medical History	X										
Concomitant Medications	X										
Eligibility Criteria	X										
Height / Weight ²	X										
Vital Signs ⁴	X	X	X	X	X	X	X	X	X	X*	X
Urine Pregnancy Test ⁵	X										
Urine Drug / Alcohol Tests	X										
Clinical Laboratory Tests ⁶	X										
Electrocardiogram ⁷	X										
Saliva – Epigenetic Test	X										
Pharmacokinetic Test ⁸	X	X	X	X	X	X	X	X	X		X

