- If, upon examination, there are questions raised about possible medical problems, the investigator can request an additional review of the participant's medical records and order additional tests or assessments, as indicated.
- Assess eligibility criteria. If the participant meets all initial screening criteria, site staff will schedule the treatment visit for Study Day 1.
- Obtain participant's ring size and dispense the health tracking wearable device and provide instruction on its use (including daily wear, recharging, etc.). If a participant has the same (or compatible) device, they can use their own.
- Each participant will take part in an introductory psilocybin preparatory session with trained staff after confirming eligibility at the initial Screening visit and prior to Study Day 1. During these sessions, participants will engage in discussions with trained facilitators about any goals or desires they have, spiritual beliefs, or world views, and any beliefs about death or the afterlife. Participants also will be asked about their intentions with the psilocybin session.

The trained staff will inform participants of what to expect during their psilocybin-assisted session. Participants will be provided with (i) information about psilocybin mushrooms, (ii) expected psychoactive and physical effects, and (iii) methods for documenting and managing side effects of psilocybin mushrooms, if/when they occur.

Information also will be shared about community support, breathing strategies, as well as rescue psychotherapy or medications available to use if needed.

- Each participant will also participate in a group education session conducted by the lead therapist regarding the treatment and ceremony following the individual preparation session.
- Participants will be instructed to bring their pain medication with them on Study Day 1 and will be educated on how their pain will be managed, including having the study site provide additional pain medication should their pain increase after the 3 doses of whole organic psilocybin chocolate are self-administered.
 - Participants who use opioid analgesics will be instructed to maintain their usual regimen.
 - Input will be obtained from the participant's regular clinical providers on appropriate pain management for the participant during the trial, particularly in the case of

CONFIDENTIAL

analgesics associated with adverse reactions of concern with psilocybin (e.g., QTc prolongation with methadone).

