- Participants will identify a trusted adult who will accompany them on their ride home and the same or another adult who will stay with them overnight at their residence after being discharged from the study site on Study Day 1.

7.1.4 Study Day 1

Study Day 1 will be scheduled after the participant completes all the required Screening Period activities and is deemed to remain eligible for treatment with the study drug. There are three portions of the Study Day 1 visit including: consist of (i) confirming eligibility and performing baseline measurements for multiple primary, secondary and exploratory endpoint assessments, prior to study drug administration, (iii) self-administration of study drug under supervision, and (iv) observing participants for 8-hours post-dose for adverse events including collection of blood samples for pharmacokinetic profiling, completing clinician rating scales, among other activities.

The following protocol mandated activities, tests, examinations, assessments and procedures will be performed on Study Day 1:

Pre-Dose and Baseline Assessments

- Inquire about any changes in the participant's health and review concomitant medications/therapies (including psychotherapy and healthcare utilization).
- Obtain vital sign measurements.
- Perform a 12-lead ECG.
- Obtain blood samples for:
 - Clinical laboratory evaluations.
 - PK profiling –30 minutes (± 2 mins).
- Obtain urine samples for:
 - Pregnancy test in women of childbearing potential.
 - Qualitative rapid urine drug screen.
 - Qualitative urine ethyl glucuronide (EtG) test to assess alcohol consumption.
- Obtain saliva sample for epigenetic analysis.
- Review all eligibility criteria.
- Issue a research participant identification card ("wallet card") that indicates they are a research participant and may test positive for drugs. The card includes the Investigator's contact information, the telephone number for a 24-hour hotline for participant support, and instructions on how/when to present the card.
- The following clinician rating scales and participant QoL and PRO instruments should be

CONFIDENTIAL

administered and/or completed by the participant, respectively:

- POMS
- BPI
- C-SSRS (category ratings of 4 or 5 will exclude the participant)
- GAD-7 (scores of ≥ 15 will exclude the participant)
- PHQ-9 (scores of ≥ 20 will exclude the participant)
- Obtain/confirm the name and telephone number of an emergency contact from the participant for use throughout the study.

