 - POMS (post-treatment score must be $\leq 125\%$ of baseline, pre-dose, value otherwise patient should be held overnight for observation)

After all assessments are completed, the effects of the study drug have dissipated and the participant is fully ambulatory, displays good balance and is psychologically stable, he/she may be discharged to home so long as they are accompanied by a trusted adult. The study site is to be notified when the participant has returned home safely, and in the absence of receiving a confirmatory phone call, study site staff will contact the participant. In addition, the participant will confirm if the same, or another, adult will stay with them overnight at their residence.

However, if the participant requires continued monitoring for one or more ongoing adverse events (including abnormal vital signs), or if the participant's assessed levels of anxiety, depression and/or suicidal ideation are found to be above pre-dose (baseline) levels, the participant should be evaluated by the Investigator (or another physician) and remain at the study site overnight for observation.

During overnight observation, the participant will be monitored by a nurse and reevaluated by the Investigator (or other physician) in the morning. The outcome of the evaluation will determine if the participant continues to participate in the trial and complete protocol-mandated, Study Day, activities. Regardless, the participant will be discharged to home on Study Day 2 only after the anxiety, depression and/or suicide ideation symptoms are at or below the respective baseline levels.

If symptoms persist, the Investigator will arrange for needed medical care including having the participant transferred to an emergency department at a nearby hospital and/or inpatient psychiatric

CONFIDENTIAL

center.

7.1.5 Study Day 2

On Study Day 2, the participant will return to the study site, as reasonably close to 24 hours after the time of study drug administration. The following protocol-mandated procedures, assessments and activities will be performed:

- Review concomitant medications
- Query the participant in a non-suggestive manner to identify any adverse events
- Obtain vital signs measurements
- Have participant join a group integration session
- Administer and/or have the participant complete the following clinical rating scales and participant QoL and PRO instruments, respectively:
 - GAD-7
 - PHQ-9
 - BPI
 - C-SSRS

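### Baseline for the exploratory scales is tied to both Screening and Day 1 pre-dose, and the two Day 1 schedules conflict on whether BPI and NIH-HEALS are collected before dosing

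*Protocol*

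**What the plan says.** **Baseline at Screening.** Section 4.1, under the Screening Period, says that some of the psychological assessments made then decide eligibility and "establish baseline measures for comparison pre- and post-treatment of exploratory objectives". The synopsis says nearly the same.

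**Baseline on Day 1 before dosing.** Section 7.1.4 describes Day 1 as including "confirming eligibility and performing baseline measurements for multiple primary, secondary and exploratory endpoint assessments, prior to study drug administration", and its sub-heading for these activities pairs pre-dose with baseline. The overnight-observation rule in the same section applies when anxiety, depression or suicidal ideation "are found to be above pre-dose (baseline) levels". The Table 1 footnote on POMS also equates baseline with the pre-dose value. The suicide-risk criterion in Section 5.1.2 treats the two as different occasions: "at Screening, or at Baseline (Visit 1".

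**Either.** The synopsis statistics read "Change in clinical and epigenetic outcomes will be measured from pre-treatment (baseline) to Study Day 7", which fits both. Sections 4.4.3 and 12.5 analyse change from baseline without naming the visit, and Section 12.5 tests each measure at p<0.05.

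**What lies between.** Screening lasts 2 to 4 weeks and can be extended (Section 4.1). Section 7.1.3 adds: "Each participant will take part in an introductory psilocybin preparatory session with trained staff after confirming eligibility". A group education session follows, and footnote 15 of Table 1 puts the individual and group sessions on separate days.

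**The concern.** This is a single-arm trial, so a change from baseline has no concurrent comparison. If the starting point is Screening, the change includes whatever happens during weeks of waiting and preparation before any study drug is taken. If it is the Day 1 pre-dose score, that period is left out. A reader of the results needs to know which applies to each scale.

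Two things in the protocol put this at risk. The text attaches the word baseline to both visits. More seriously, the two Day 1 schedules disagree on which scales are taken before dosing. A pre-dose score that was not collected cannot be recovered after dosing, whatever an analysis plan later says.

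**Working it through.** **Step 1: compare the schedules.** Sources: Table 1 and Section 7.1.3 for Screening; Table 2 and the pre-dose list in Section 7.1.4 for Day 1.

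| Scale | Screening | Day 1 pre-dose, Table 2 | Day 1 pre-dose, Section 7.1.4 |
|---|---|---|---|
| GAD-7, PHQ-9, C-SSRS | yes | yes | yes |
| POMS | no | yes | yes |
| NIH-HEALS | yes | yes | **no** |
| BPI | yes | **no** (8 hours only) | yes |
| SDS, AUDIT, DUDIT | yes | no | no |
| PCL-5 | yes | no | no |

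Four scales agree before dosing on Day 1 and two conflict. Table 1 puts BPI and NIH-HEALS on Day 1 without separating pre-dose from post-dose, so it does not settle the matter. The single BPI mark in Table 2 lines up with WCS, MEQ30, CEQ and 5D-ASC, which Section 7.1.4 also lists only near 8 hours. A misread table is therefore an unlikely explanation. NIH-HEALS is missing from both the pre-dose and the 8-hour lists in Section 7.1.4.

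**Step 2: check that the weeks are real.** Screening of 14 to 28 days plus 90 days gives 104 to 118 days. At 30.44 days per month that is 3.4 to 3.9 months, in line with the 3.5 to 4.0 months in Section 4.3.

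**Step 3: share of the baseline-to-visit interval that precedes dosing, if Screening is baseline.** Share = s/(s+v), where s is days of Screening and v is days from dosing to the visit. This assumes that the scales are completed at the initial Screening visit, where Section 7.1.3 lists them.

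| Visit | v | s = 14 | s = 28 |
|---|---|---|---|
| Day 8 | 7 | 14/21 = 67% | 28/35 = 80% |
| Day 30 | 29 | 14/43 = 33% | 28/57 = 49% |
| Day 90 | 89 | 14/103 = 14% | 28/117 = 24% |

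With the Day 1 pre-dose score as baseline, every share is zero. An extended Screening Period raises the figures above.

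**Step 4: what pre-dose drift could do to a p<0.05 test.** The protocol gives no drift, so this is an illustration under assumed values. Take n = 24, no drug effect, a two-sided 5% paired t test standing in for the planned model, and a Screening-to-Day-1 drift of d standard deviations of the change score. The noncentrality is d×√24, on 23 degrees of freedom.

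| d | Noncentrality | Trials with p<0.05 |
|---|---|---|
| 0 | 0 | 5% |
| 0.1 | 0.49 | 7.6% |
| 0.2 | 0.98 | 15.6% |
| 0.3 | 1.47 | 29.1% |
| 0.5 | 2.45 | 65.0% |

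**The case against.** The best reply is that both statements can be true for different instruments. Section 4.1 says only that some Screening assessments serve as baseline, and for SDS, AUDIT and DUDIT there is no other pre-dose value. Section 7.1.4 speaks of multiple endpoint assessments, not all. For scales taken at both visits, most of the text points to Day 1. The choice of analysis baseline can also be left to the SAP.

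Much of this stands, and it limits the point. It would be too strong to infer that baseline is contradictory for every exploratory scale. But Section 4.1 does not say which scales it means, and an SAP cannot supply a pre-dose BPI or NIH-HEALS score that was never collected.

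Three other stronger readings are tempting and are not supported:

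- **That the entry cut-offs flatter the drug, and more so from Screening.** For GAD-7 the rule is: "If a participant's score is ≥15 at Screening or on Study Day 1 (prior to study drug administration), the participant is not eligible for treatment". Because the cap applies alike at both visits, in a stable population it gives no expected change between them, and the same later shift from either. Since it removes high scores, that shift is towards worsening. The one minimum symptom score for entry is on PCL-5, which is not repeated after Screening and so has no change score.
- **That an untreated lead-in goes unused.** The period contains preparatory sessions, and Section 6.7.2 permits psychotherapy, so it is only a period before study drug. Section 12.5 summarises questionnaires by visit, the wearable is dispensed at Screening and may supply its own baseline, and an SAP that is not at hand may use the rest.
- **That preliminary efficacy should be redefined as change in excess of the Screening-to-Day-1 change.** Dosed participants are partly selected on Day 1 scores, and a lead-in of 2 to 4 weeks does not match follow-up at Days 2, 4, 8, 30 and 90. Subtraction also adds noise. With independent errors of equal variance, a simple change carries 2 units of error variance. Post-dose minus twice Day 1 plus Screening carries 1 + 4 + 1 = 6.

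**Conclusion.** The point holds in limited form. The conflict between Table 2 and Section 7.1.4 is definite and covers two scales, BPI and NIH-HEALS. Following either schedule alone loses one Day 1 pre-dose value. For that scale, the change at Day 8 would cover 21 to 35 days, of which 67% to 80% precede study drug. These figures rest on the stated 2 to 4 weeks and on the scales being completed at the initial Screening visit; scales completed later in Screening would shorten the gap.

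The double use of the word baseline is a looseness to be cleared up. For GAD-7, PHQ-9 and C-SSRS the Day 1 pre-dose scores exist under both schedules. The rejection rates in Step 4 depend wholly on the assumed drift, whose size and direction the protocol does not give.

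Only exploratory endpoints are touched. The primary safety and secondary pharmacokinetic endpoints do not depend on these scales. The correction should still be made before participants are dosed, because the missing scores cannot be obtained afterwards.

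**What to change.** 1. Make Table 2 and the pre-dose list in Section 7.1.4 identical, with both BPI and NIH-HEALS before dosing on Day 1.
2. State in Sections 4.1 and 4.4.3 that baseline is the last pre-dose value: Day 1 for scales collected then, Screening for SDS, AUDIT and DUDIT. Note that PCL-5 is not repeated after Screening and has no change score.
3. Optionally, show the Screening-to-Day-1 change for the twice-measured scales descriptively beside the post-dose change, without subtracting it.

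The cost is wording, at most one questionnaire before dosing that one of the two schedules already requires, and one table column if the third item is taken up. The rule in item 2 gives no baseline for WCS, MEQ30, CEQ and 5D-ASC. Neither schedule collects them before dosing, although Section 4.4.3 lists them for change from baseline. That needs separate attention.
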